1. INTRODUCTION

This supplemental statistical analysis plan (SAP) describes the methods for exploratory efficacy analyses conducted after the primary analysis. Assessments of relative vaccine efficacy (rVE) analysis of booster vaccination with Ad26.COV2.S of the (i) heterologous booster compared to homologous booster vaccination at the same dose level; (ii) within each Cohort, dose levels (Ad26.COV2.S 5×10^{10} vp and 2.5×10^{10} vp) versus the lower dose level (Ad26.COV2.S 1×10^{10} vp) will be conducted.

This SAP is based on Clinical Trial Protocol (CTP) VAC31518COV2008 Amendment 6. For main SAP please refer to document EDMS RIM-462169 dated 15Dec2021. Data Presentation Specification (DPS) documents that further detail the planned statistical outputs are available.

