5.1.3. Scope of Analysis of the Relative Vaccine Efficacy

The rVE analysis is planned to compare heterologous to homologous vaccination with same dose level, and within each cohort the two higher dose levels (i.e., Ad26.COV2.S 5×10^{10} vp and 2.5×10^{10} vp) to the lower dose level (i.e., 1×10^{10} vp). The analysis will include efficacy data collected during the study until database cut-off or study discontinuation of the participant.

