5.3. Exploratory Endpoint(s) Analysis

5.3.1. Definition of Endpoints and Estimands

5.3.1.1. Exploratory endpoint(s)

The exploratory endpoint(s) is defined as a COVID-19 case meeting case definitions, as defined in Sections 5.2.4 and 5.2.5, with onset at least 14 days post last vaccination.

Estimand 1:

What is the relative vaccine efficacy against moderate to severe/critical COVID-19 of Ad26.COV2.S booster vaccination at different dose levels within and between cohorts in adults ≥ 18 years with or without comorbidities associated with increased risk of progression to severe COVID-19?

Population: Adults ≥ 18 years with or without comorbidities associated with increased risk of progression to severe COVID-19 cases and who previously received primary vaccination with Ad26.COV2.S or BNT162b2 and subsequently received Ad26.COV2.S boost on the study.

Endpoint: Molecularly confirmed symptomatic moderate to severe/critical COVID-19 Omicron infections with onset ≥ 14 days after last study vaccination.

Intercurrent Events: Other COVID-19 vaccines.

Data handling for estimators: Cases will be counted from the day after last Ad26.COV2.S vaccination until and including the last available timepoint in the database. Participants with a SARS-CoV-2 infection (symptomatic or asymptomatic) prior to 14 days post last study vaccination will be excluded from the risk set.

A subject will be censored:

- If no event of interest to the analysis was experienced during the considered observation period
- On the date of receipt of another authorized/approved COVID-19 vaccine outside of the study, the date of study discontinuation or the last available date (data lock point), whichever occurred first.

The above defined Estimand approach will be used for following interventions and summary measures:

Estimand	Interventions	Summary Measures ¹
Within each Cohort: (Cohort 1 and 2 separately)		
Estimand 1.1	Ad26.COV2.S 5×10^{10} vp and Ad26.COV2.S 1×10^{10} vp	Relative VE = 100 x (1-hazard ratio of Ad26.COV2.S 5×10^{10} vp / Ad26.COV2.S 1×10^{10} vp)%
Estimand 1.2	Ad26.COV2.S 2.5×10^{10} vp and Ad26.COV2.S 1×10^{10} vp	Relative VE = 100 x (1-hazard ratio of incidence Ad26.COV2.S 2.5×10^{10} vp / Ad26.COV2.S 1×10^{10} vp)%
Between Cohorts:		
Estimand 1.3	Ad26.COV2.S 5×10^{10} vp (Cohort 1) and Ad26.COV2.S 5×10^{10} vp (Cohort 2)	Relative VE = 100 x (1-hazard ratio of Cohort 1 Ad26.COV2.S 5×10^{10} vp / Cohort 2 Ad26.COV2.S 5×10^{10} vp)%

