Estimand 1.4	Ad26.COV2.S 2.5×10^{10} vp (Cohort 1) and Ad26.COV2.S 2.5×10^{10} vp (Cohort 2)	Relative VE = 100 x (1-hazard ratio of Cohort 1 Ad26.COV2.S 2.5×10^{10} vp / Cohort 2 Ad26.COV2.S 2.5×10^{10} vp)%
Estimand 1.5	Ad26.COV2.S 1×10^{10} vp (Cohort 1) and Ad26.COV2.S 1×10^{10} vp (Cohort 2)	Relative VE = 100 x (1-hazard ratio of Cohort 1 Ad26.COV2.S 1×10^{10} vp / Cohort 2 Ad26.COV2.S 1×10^{10} vp)%

¹Relative VE and associated 95% CI will be calculated from Cox Proportional hazards model.

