5.3.2. Analysis Method

Exploratory analysis will be done on the PPE analysis set including only baseline seronegative subjects. The analysis will focus on the Omicron variant, as this is presumed to be the dominant variant during the observation period.

Analysis will be performed if there are at least 6 cases available for the analysis of interest.

i) Calendar-Based Time Scale Method:

For the exploratory efficacy endpoints, follow-up time will be expressed on a calendar time scale, and is defined as time since study start (i.e., 08 August 2021) to adjust for changing incidence over time. Follow-up time will begin on the date of administration of the first dose of Janssen COVID-19 vaccine (within study COV2008), expressed on a calendar time scale as time since study start,

although follow-up time and events occurring within 14 days post vaccination with first dose of Janssen COVID-19 vaccine will be ignored.

The follow-up time is the time to first occurrence of moderate to severe disease, with an onset at any time at least 14 days post vaccination of previously received Janssen COVID-19 vaccine. An individual will be censored at i) the date of receipt of another authorized/approved COVID-19 vaccine, including the Janssen COVID-19 vaccine if received outside of the study, ii) the date of study discontinuation, or iii) the last available date, whichever occurred first.

Vaccine efficacy will be summarized by relative vaccine efficacy measures and the associated 95% confidence intervals (CI) using time-dependent Cox Proportional hazards models , stratified by the following factors to account for i) changing incidence over calendar time, ii) potential confounding by age [18 - <60 years (as reference category), ≥ 60 years], co-morbidities [Y/N (as a reference category)] and geographical region in which the site is located (cf. Section 5.4.1).

One model will be fit estimating VE under the assumption of constant relative vaccine efficacy (Fintzi et al, 2020), comparing:

- Within each Cohort, from higher dose levels (i.e. Ad26.COV2.S 5×10^{10} vp and 2.5×10^{10} vp) to lower dose level (Ad26.COV2.S 1×10^{10} vp).
- Heterologous booster (Cohort 2) to homologous booster (Cohort 1) vaccination at same dose level.

Models that do not converge will be omitted and reported as non-convergent. The method for tabulating relative VE and 95% CI will be detailed in DPS.

Estimand 2:

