What is the relative vaccine efficacy against moderate COVID-19 of Ad26.COV2.S booster vaccination at different dose levels within and between cohorts in adults ≥ 18 years with or without comorbidities associated with increased risk of progression to moderate COVID-19?

Population: Adults ≥ 18 years with or without comorbidities associated with increased risk of progression to severe COVID-19 cases and who previously received primary vaccination with Ad26.COV2.S or BNT162b2 and subsequently received Ad26.COV2.S boost on the study.

Endpoint: Molecularly confirmed symptomatic moderate COVID-19 Omicron infections with onset ≥ 14 days after last study vaccination.

Intercurrent Events: Other COVID-19 vaccines

Data handling for estimators: Cases will be counted from the day after last Ad26.COV2.S vaccination until and including the last available timepoint in the database. Participants with a SARS-CoV-2 infection (symptomatic or asymptomatic) prior to 14 days post last study vaccination will be excluded from the risk set.

A subject will be censored:

- If no event of interest to the analysis was experienced during the considered observation period
- On the date of receipt of another authorized/approved COVID-19 vaccine outside of the study, the date of study discontinuation or the last available date (data lock point), whichever occurred first.

The above defined Estimand approach will be used for following interventions and summary measures:

Estimand	Interventions	Summary Measures ¹
Within each Cohort: (Cohort 1 and 2 separately)		
Estimand 2.1	Ad26.COV2.S 5×10^{10} vp and Ad26.COV2.S 1×10^{10} vp	Relative VE = 100 x (1-hazard ratio of Ad26.COV2.S 5×10^{10} vp / Ad26.COV2.S 1×10^{10} vp)%
Estimand 2.2	Ad26.COV2.S 2.5×10^{10} vp and Ad26.COV2.S 1×10^{10} vp	Relative VE = 100 x (1-hazard ratio of incidence Ad26.COV2.S 2.5×10^{10} vp / Ad26.COV2.S 1×10^{10} vp)%
Between Cohorts:		
Estimand 2.3	Ad26.COV2.S 5×10^{10} vp (Cohort 1) and Ad26.COV2.S 5×10^{10} vp (Cohort 2)	Relative VE = 100 x (1-hazard ratio of Cohort 1 Ad26.COV2.S 5×10^{10} vp / Cohort 2 Ad26.COV2.S 5×10^{10} vp)%
Estimand 2.4	Ad26.COV2.S 2.5×10^{10} vp (Cohort 1) and Ad26.COV2.S 2.5×10^{10} vp (Cohort 2)	Relative VE = 100 x (1-hazard ratio of Cohort 1 Ad26.COV2.S 2.5×10^{10} vp / Cohort 2 Ad26.COV2.S 2.5×10^{10} vp)%

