Estimand 4.2	Ad26.COV2.S 2.5×10^{10} vp and Ad26.COV2.S 1×10^{10} vp	Relative VE = $100 \times (1 - \text{hazard ratio of incidence Ad26.COV2.S } 2.5 \times 10^{10} \text{ vp} / \text{Ad26.COV2.S } 1 \times 10^{10} \text{ vp})\%$
Between Cohorts:		
Estimand 4.3	Ad26.COV2.S 5×10^{10} vp (Cohort 1) and Ad26.COV2.S 5×10^{10} vp (Cohort 2)	Relative VE = $100 \times (1 - \text{hazard ratio of Cohort 1 Ad26.COV2.S } 5 \times 10^{10} \text{ vp} / \text{Cohort 2 Ad26.COV2.S } 5 \times 10^{10} \text{ vp})\%$
Estimand 4.4	Ad26.COV2.S 2.5×10^{10} vp (Cohort 1) and Ad26.COV2.S 2.5×10^{10} vp (Cohort 2)	Relative VE = $100 \times (1 - \text{hazard ratio of Cohort 1 Ad26.COV2.S } 2.5 \times 10^{10} \text{ vp} / \text{Cohort 2 Ad26.COV2.S } 2.5 \times 10^{10} \text{ vp})\%$
Estimand 4.5	Ad26.COV2.S 1×10^{10} vp (Cohort 1) and Ad26.COV2.S 1×10^{10} vp (Cohort 2)	Relative VE = $100 \times (1 - \text{hazard ratio of Cohort 1 Ad26.COV2.S } 1 \times 10^{10} \text{ vp} / \text{Cohort 2 Ad26.COV2.S } 1 \times 10^{10} \text{ vp})\%$

¹Relative VE and associated 95% CI will be calculated from Cox Proportional hazards model.

Analysis method will be repeated as explained in Section 5.3.2.

Estimand 5:

What is the relative vaccine efficacy against asymptomatic/undetected COVID-19 of Ad26.COV2.S booster vaccination at different dose levels within and between cohorts in adults ≥ 18 years with or without comorbidities associated with increased risk of progression to severe COVID-19?

Population: Adults ≥ 18 years with or without comorbidities associated with increased risk of progression to severe COVID-19 cases and who previously received primary vaccination with Ad26.COV2.S or BNT162b2 and subsequently received Ad26.COV2.S boost on the study.

Endpoint: Asymptomatic/undetected COVID-19 Omicron infections with onset ≥ 14 days after last study vaccination.

Intercurrent Events: Other COVID-19 vaccines

Data handling for estimators: Cases will be counted from the day after last Ad26.COV2.S vaccination until and including the last available timepoint in the database. Participants with a SARS-CoV-2 infection (asymptomatic/undetected) prior to 14 days post last study vaccination will be excluded from the risk set.

A subject will be censored:

- If no event of interest to the analysis was experienced during the considered observation period

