5.6. Safety Analyses

All safety analyses will be based on the FAS based on actual intervention received, unless otherwise specified.

All continuous safety variables, descriptive statistics by intervention group will include the N, mean, standard deviation, median, minimum, and maximum. Categorical variables will be summarized by vaccination group using frequency counts and percentages. All safety data summary will be presented by Cohort where Cohort 1 includes participants who received Ad26.COV2.S as primary vaccination; and Cohort 2 includes those who received BNT162b2 as primary vaccination, unless specified otherwise. In addition, selected safety results will be presented in the same output with both cohorts.

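### All 15 between-cohort estimands define relative VE as homologous over heterologous, the inverse of the stated objective and of the model description

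*SAP*

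**What the plan says.** The supplemental SAP states the direction of the between-cohort comparison in four places, all consistent with one another:

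- Section 1 (Introduction): "heterologous booster compared to homologous booster vaccination at the same dose level".
- Section 1.1, first exploratory objective: rVE of the heterologous booster, compared with the homologous booster at each dose level.
- Section 5.1.3: the analysis is to "compare heterologous to homologous vaccination with same dose level".
- Section 5.3.2, where the Cox model is described: "Heterologous booster (Cohort 2) to homologous booster (Cohort 1) vaccination at same dose level".

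The cohort labels are not in doubt. Section 5.3.2 names them, and section 5.6 of the main SAP confirms that "Cohort 1 includes participants who received Ad26.COV2.S as primary vaccination", so an Ad26.COV2.S booster is homologous in Cohort 1. Cohort 2 had BNT162b2 as primary vaccination, so the same booster is heterologous there.

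The estimand tables give the formal summary measure. For Estimand 1.3 it starts "Relative VE = 100 x (1-hazard ratio of Cohort 1 Ad26.COV2.S" and has the Cohort 2 arm as denominator. Estimand 1.4 uses the "hazard ratio of Cohort 1 Ad26.COV2.S 2.5×10^{10} vp / Cohort 2 Ad26.COV2.S 2.5×10^{10} vp" and Estimand 2.3 the "hazard ratio of Cohort 1 Ad26.COV2.S 5×10^{10} vp / Cohort 2 Ad26.COV2.S 5×10^{10} vp". The remaining between-cohort rows follow the same pattern.

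**The concern.** Four passages make the heterologous booster the evaluated arm, while every between-cohort formula makes it the reference. As tabulated, these rows give the rVE of the homologous booster relative to the heterologous one.

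The direction matters because rVE is 1 − HR, which is not symmetric when the ratio is inverted: the sign, the size and both confidence limits change. If outputs are programmed from the tables, a better heterologous booster appears as a large negative rVE. Anyone reading that number against the objective would conclude the opposite of what the data show. The comparison at issue is the first objective of the supplemental SAP, and it is affected for every endpoint and dose level.

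**Working it through.** **1. Direction in the text and in the tables**

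| Place (supplemental SAP) | Evaluated arm | Reference |
|---|---|---|
| Section 1, Introduction | heterologous | homologous |
| Section 1.1, first objective | heterologous | homologous |
| Section 5.1.3, scope | heterologous | homologous |
| Section 5.3.2, model description | Cohort 2 (heterologous) | Cohort 1 (homologous) |
| Estimand tables, rows x.3 to x.5 | Cohort 1 (homologous) | Cohort 2 (heterologous) |

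**2. Convention within the tables.** Rows x.1 and x.2 put the higher dose in the numerator and the 1×10^10 vp dose in the denominator. This matches section 5.3.2, which compares the higher doses to the lower one. Reading the next item of section 5.3.2 in the same way requires Cohort 2 / Cohort 1. Only the between-cohort rows depart from the pattern.

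**3. Count.** The between-cohort rows are 1.3–1.5, 2.3–2.5, 3.3–3.5, 4.3–4.5 and 5.3–5.5: 5 endpoints × 3 dose levels = 15. With two within-cohort rows per endpoint (each counted once), the tables list 5 × 5 = 25 rows, so 15 of 25 are inverted. None of the 15 is written the other way.

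**4. Effect of the inversion.** Let HR be heterologous / homologous.

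- Objective: rVE = 100 × (1 − HR)
- Tables as written: rVE = 100 × (1 − 1/HR)

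The SAP gives no expected HR for this contrast, so the values below are assumptions across a range.

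| Assumed HR | rVE by the objective | rVE by the tables |
|---|---|---|
| 0.5 | +50% | −100% |
| 0.7 | +30% | −42.9% |
| 0.8 | +20% | −25% |
| 1.0 | 0% | 0% |
| 1.25 | −25% | +20% |
| 2.0 | −100% | +50% |

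With an assumed CI of 0.30 to 0.83 around HR 0.5:

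- Objective: 1 − 0.83 = 17% to 1 − 0.30 = 70%.
- Tables: 1 − 1/0.30 = −233% to 1 − 1/0.83 = −20%.

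The two signs are opposite for every HR other than 1. In the last line of the table, a heterologous booster with twice the hazard would be reported as +50%.

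**The case against.** The strongest counter-argument concerns consequence. The reversal occurs only if programming follows the estimand tables. The model description in section 5.3.2 has the intended direction, and that section leaves the tabulation of rVE and its CI to the DPS, which is not at hand. Each row also names its numerator and denominator, so a correctly labelled output would be a valid answer to the mirror-image question, and the estimate and both limits convert exactly through 1/HR. The analyses are exploratory. No success criterion or alpha depends on them, and whether the interval excludes 0% is the same in either direction. The example hazard ratios are not taken from the SAP.

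All of that stands, and it limits the damage. It does not remove the contradiction. The estimand table is the formal definition of the summary measure, and analysts working from different sections would produce results of opposite sign. Exact conversion helps only a reader who notices the inversion, and changing the sign alone does not give the right value. Leaving the direction to the DPS would keep two opposite definitions in the SAP.

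**Conclusion.** The concern holds. All 15 between-cohort summary measures are written as the inverse of what the introduction, the objective, the scope section and the model description specify, and they also break the convention of the within-cohort rows beside them. If outputs follow the tables, every heterologous-versus-homologous rVE changes sign (unless HR = 1) and size: for an assumed HR of 0.5, −100% in place of +50%. The count and the direction come straight from the SAP; the percentages rest on assumed hazard ratios and show how the inversion works, not an expected result. Tests of HR = 1 and the within-cohort dose comparisons are unaffected. Although the analyses are exploratory, this must be corrected before outputs are produced, because the direction determines how the whole between-cohort block is read.

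**What to change.** - In Estimands x.3, x.4 and x.5 for x = 1 to 5, rewrite the hazard ratio as Cohort 2 over Cohort 1 at the same dose level.
- State once, in section 5.3.1.1 or 5.3.2, that the homologous booster (Cohort 1) is the reference for all between-cohort comparisons, so that a positive rVE favours the heterologous booster.
- Align the DPS and label each output with its numerator and denominator.

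The cost is SAP wording and table shells. Data collection, the design, the Cox model and the risk sets do not change.

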5.3.2. Analysis Method

Exploratory analysis will be done on the PPE analysis set including only baseline seronegative subjects. The analysis will focus on the Omicron variant, as this is presumed to be the dominant variant during the observation period.

Analysis will be performed if there are at least 6 cases available for the analysis of interest.

i) Calendar-Based Time Scale Method:

For the exploratory efficacy endpoints, follow-up time will be expressed on a calendar time scale, and is defined as time since study start (i.e., 08 August 2021) to adjust for changing incidence over time. Follow-up time will begin on the date of administration of the first dose of Janssen COVID-19 vaccine (within study COV2008), expressed on a calendar time scale as time since study start,

although follow-up time and events occurring within 14 days post vaccination with first dose of Janssen COVID-19 vaccine will be ignored.

The follow-up time is the time to first occurrence of moderate to severe disease, with an onset at any time at least 14 days post vaccination of previously received Janssen COVID-19 vaccine. An individual will be censored at i) the date of receipt of another authorized/approved COVID-19 vaccine, including the Janssen COVID-19 vaccine if received outside of the study, ii) the date of study discontinuation, or iii) the last available date, whichever occurred first.

Vaccine efficacy will be summarized by relative vaccine efficacy measures and the associated 95% confidence intervals (CI) using time-dependent Cox Proportional hazards models , stratified by the following factors to account for i) changing incidence over calendar time, ii) potential confounding by age [18 - <60 years (as reference category), ≥ 60 years], co-morbidities [Y/N (as a reference category)] and geographical region in which the site is located (cf. Section 5.4.1).

One model will be fit estimating VE under the assumption of constant relative vaccine efficacy (Fintzi et al, 2020), comparing:

- Within each Cohort, from higher dose levels (i.e. Ad26.COV2.S 5×10^{10} vp and 2.5×10^{10} vp) to lower dose level (Ad26.COV2.S 1×10^{10} vp).
- Heterologous booster (Cohort 2) to homologous booster (Cohort 1) vaccination at same dose level.

Models that do not converge will be omitted and reported as non-convergent. The method for tabulating relative VE and 95% CI will be detailed in DPS.

Estimand 2:

What is the relative vaccine efficacy against moderate COVID-19 of Ad26.COV2.S booster vaccination at different dose levels within and between cohorts in adults ≥ 18 years with or without comorbidities associated with increased risk of progression to moderate COVID-19?

Population: Adults ≥ 18 years with or without comorbidities associated with increased risk of progression to severe COVID-19 cases and who previously received primary vaccination with Ad26.COV2.S or BNT162b2 and subsequently received Ad26.COV2.S boost on the study.

Endpoint: Molecularly confirmed symptomatic moderate COVID-19 Omicron infections with onset ≥ 14 days after last study vaccination.

Intercurrent Events: Other COVID-19 vaccines

Data handling for estimators: Cases will be counted from the day after last Ad26.COV2.S vaccination until and including the last available timepoint in the database. Participants with a SARS-CoV-2 infection (symptomatic or asymptomatic) prior to 14 days post last study vaccination will be excluded from the risk set.

A subject will be censored:

- If no event of interest to the analysis was experienced during the considered observation period
- On the date of receipt of another authorized/approved COVID-19 vaccine outside of the study, the date of study discontinuation or the last available date (data lock point), whichever occurred first.

The above defined Estimand approach will be used for following interventions and summary measures:

Estimand	Interventions	Summary Measures ¹
Within each Cohort: (Cohort 1 and 2 separately)		
Estimand 2.1	Ad26.COV2.S 5×10^{10} vp and Ad26.COV2.S 1×10^{10} vp	Relative VE = 100 x (1-hazard ratio of Ad26.COV2.S 5×10^{10} vp / Ad26.COV2.S 1×10^{10} vp)%
Estimand 2.2	Ad26.COV2.S 2.5×10^{10} vp and Ad26.COV2.S 1×10^{10} vp	Relative VE = 100 x (1-hazard ratio of incidence Ad26.COV2.S 2.5×10^{10} vp / Ad26.COV2.S 1×10^{10} vp)%
Between Cohorts:		
Estimand 2.3	Ad26.COV2.S 5×10^{10} vp (Cohort 1) and Ad26.COV2.S 5×10^{10} vp (Cohort 2)	Relative VE = 100 x (1-hazard ratio of Cohort 1 Ad26.COV2.S 5×10^{10} vp / Cohort 2 Ad26.COV2.S 5×10^{10} vp)%
Estimand 2.4	Ad26.COV2.S 2.5×10^{10} vp (Cohort 1) and Ad26.COV2.S 2.5×10^{10} vp (Cohort 2)	Relative VE = 100 x (1-hazard ratio of Cohort 1 Ad26.COV2.S 2.5×10^{10} vp / Cohort 2 Ad26.COV2.S 2.5×10^{10} vp)%
Estimand 2.5	Ad26.COV2.S 1×10^{10} vp (Cohort 1) and Ad26.COV2.S 1×10^{10} vp (Cohort 2)	Relative VE = 100 x (1-hazard ratio of Cohort 1 Ad26.COV2.S 1×10^{10} vp / Cohort 2 Ad26.COV2.S 1×10^{10} vp)%

¹Relative VE and associated 95% CI will be calculated from Cox Proportional hazards model.

Analysis method will be repeated as explained in Section [5.3.2](#).

Estimand 3:

What is the relative vaccine efficacy against severe/critical COVID-19 of Ad26.COV2.S booster vaccination at different dose levels within and between cohorts in adults ≥ 18 years with or without comorbidities associated with increased risk of progression to severe COVID-19?

Population: Adults ≥ 18 years with or without comorbidities associated with increased risk of progression to severe COVID-19 cases and who previously received primary vaccination with Ad26.COV2.S or BNT162b2 and subsequently received Ad26.COV2.S boost on the study.

Endpoint: Molecularly confirmed symptomatic severe/critical COVID-19 Omicron infections with onset ≥ 14 days after last study vaccination.

Intercurrent Events: Other COVID-19 vaccines

Data handling for estimators: Cases will be counted from the day after last Ad26.COV2.S vaccination until and including the last available timepoint in the database. Participants with a SARS-CoV-2 infection (symptomatic or asymptomatic) prior to 14 days post last study vaccination will be excluded from the risk set.

A subject will be censored:

- If no event of interest to the analysis was experienced during the considered observation period
- On the date of receipt of another authorized/approved COVID-19 vaccine outside of the study, the date of study discontinuation or the last available date (data lock point), whichever occurred first.

The above defined Estimand approach will be used for following interventions and summary measures:

Estimand	Interventions	Summary Measures ¹
Within each Cohort: (Cohort 1 and 2 separately)		
Estimand 3.1	Ad26.COV2.S 5×10^{10} vp and Ad26.COV2.S 1×10^{10} vp	Relative VE = 100 x (1-hazard ratio of Ad26.COV2.S 5×10^{10} vp / Ad26.COV2.S 1×10^{10} vp)%
Estimand 3.2	Ad26.COV2.S 2.5×10^{10} vp and Ad26.COV2.S 1×10^{10} vp	Relative VE = 100 x (1-hazard ratio of incidence Ad26.COV2.S 2.5×10^{10} vp / Ad26.COV2.S 1×10^{10} vp)%
Between Cohorts:		
Estimand 3.3	Ad26.COV2.S 5×10^{10} vp (Cohort 1) and Ad26.COV2.S 5×10^{10} vp (Cohort 2)	Relative VE = 100 x (1-hazard ratio of Cohort 1 Ad26.COV2.S 5×10^{10} vp / Cohort 2 Ad26.COV2.S 5×10^{10} vp)%
Estimand 3.4	Ad26.COV2.S 2.5×10^{10} vp (Cohort 1) and Ad26.COV2.S 2.5×10^{10} vp (Cohort 2)	Relative VE = 100 x (1-hazard ratio of Cohort 1 Ad26.COV2.S 2.5×10^{10} vp / Cohort 2 Ad26.COV2.S 2.5×10^{10} vp)%
Estimand 3.5	Ad26.COV2.S 1×10^{10} vp (Cohort 1) and Ad26.COV2.S 1×10^{10} vp (Cohort 2)	Relative VE = 100 x (1-hazard ratio of Cohort 1 Ad26.COV2.S 1×10^{10} vp / Cohort 2 Ad26.COV2.S 1×10^{10} vp)%

¹Relative VE and associated 95% CI will be calculated from Cox Proportional hazards model.

Analysis method will be repeated as explained in Section [5.3.2](#).

Estimand 4:

What is the relative vaccine efficacy against US FDA Harmonized COVID-19 of Ad26.COV2.S booster vaccination at different dose levels within and between cohorts in adults ≥ 18 years with or without comorbidities associated with increased risk of progression to severe COVID-19?

Population: Adults ≥ 18 years with or without comorbidities associated with increased risk of progression to severe COVID-19 cases and who previously received primary vaccination with Ad26.COV2.S or BNT162b2 and subsequently received Ad26.COV2.S boost on the study.

Endpoint: Molecularly confirmed symptomatic US FDA Harmonized COVID-19 Omicron infections with onset ≥ 14 days after last study vaccination.

Intercurrent Events: Other COVID-19 vaccines

Data handling for estimators: Cases will be counted from the day after last Ad26.COV2.S vaccination until and including the last available timepoint in the database. Participants with a SARS-CoV-2 infection (symptomatic or asymptomatic) related to US FDA Harmonized COVID-19 prior to 14 days post last study vaccination will be excluded from the risk set.

A subject will be censored:

- If no event of interest to the analysis was experienced during the considered observation period
- On the date of receipt of another authorized/approved COVID-19 vaccine outside of the study, the date of study discontinuation or the last available date (data lock point), whichever occurred first.

The above defined Estimand approach will be used for following interventions and summary measures:

Estimand	Interventions	Summary Measures ¹
Within each Cohort: (Cohort 1 and 2 separately)		
Estimand 4.1	Ad26.COV2.S 5×10^{10} vp and Ad26.COV2.S 1×10^{10} vp	Relative VE = $100 \times (1 - \text{hazard ratio of Ad26.COV2.S } 5 \times 10^{10} \text{ vp} / \text{Ad26.COV2.S } 1 \times 10^{10} \text{ vp})\%$
Estimand 4.2	Ad26.COV2.S 2.5×10^{10} vp and Ad26.COV2.S 1×10^{10} vp	Relative VE = $100 \times (1 - \text{hazard ratio of incidence Ad26.COV2.S } 2.5 \times 10^{10} \text{ vp} / \text{Ad26.COV2.S } 1 \times 10^{10} \text{ vp})\%$
Between Cohorts:		
Estimand 4.3	Ad26.COV2.S 5×10^{10} vp (Cohort 1) and Ad26.COV2.S 5×10^{10} vp (Cohort 2)	Relative VE = $100 \times (1 - \text{hazard ratio of Cohort 1 Ad26.COV2.S } 5 \times 10^{10} \text{ vp} / \text{Cohort 2 Ad26.COV2.S } 5 \times 10^{10} \text{ vp})\%$
Estimand 4.4	Ad26.COV2.S 2.5×10^{10} vp (Cohort 1) and Ad26.COV2.S 2.5×10^{10} vp (Cohort 2)	Relative VE = $100 \times (1 - \text{hazard ratio of Cohort 1 Ad26.COV2.S } 2.5 \times 10^{10} \text{ vp} / \text{Cohort 2 Ad26.COV2.S } 2.5 \times 10^{10} \text{ vp})\%$
Estimand 4.5	Ad26.COV2.S 1×10^{10} vp (Cohort 1) and Ad26.COV2.S 1×10^{10} vp (Cohort 2)	Relative VE = $100 \times (1 - \text{hazard ratio of Cohort 1 Ad26.COV2.S } 1 \times 10^{10} \text{ vp} / \text{Cohort 2 Ad26.COV2.S } 1 \times 10^{10} \text{ vp})\%$

¹Relative VE and associated 95% CI will be calculated from Cox Proportional hazards model.

Analysis method will be repeated as explained in Section 5.3.2.

Estimand 5:

What is the relative vaccine efficacy against asymptomatic/undetected COVID-19 of Ad26.COV2.S booster vaccination at different dose levels within and between cohorts in adults ≥ 18 years with or without comorbidities associated with increased risk of progression to severe COVID-19?

Population: Adults ≥ 18 years with or without comorbidities associated with increased risk of progression to severe COVID-19 cases and who previously received primary vaccination with Ad26.COV2.S or BNT162b2 and subsequently received Ad26.COV2.S boost on the study.

Endpoint: Asymptomatic/undetected COVID-19 Omicron infections with onset ≥ 14 days after last study vaccination.

Intercurrent Events: Other COVID-19 vaccines

Data handling for estimators: Cases will be counted from the day after last Ad26.COV2.S vaccination until and including the last available timepoint in the database. Participants with a SARS-CoV-2 infection (asymptomatic/undetected) prior to 14 days post last study vaccination will be excluded from the risk set.

A subject will be censored:

- If no event of interest to the analysis was experienced during the considered observation period
- On the date of receipt of another authorized/approved COVID-19 vaccine outside of the study, the date of study discontinuation or the last available date (data lock point), whichever occurred first.

The above defined Estimand approach will be used for following interventions and summary measures:

Estimand	Interventions	Summary Measures ¹
Within each Cohort: (Cohort 1 and 2 separately)		
Estimand 5.1	Ad26.COV2.S 5×10^{10} vp and Ad26.COV2.S 1×10^{10} vp	Relative VE = $100 \times (1 - \text{hazard ratio of Ad26.COV2.S } 5 \times 10^{10} \text{ vp} / \text{Ad26.COV2.S } 1 \times 10^{10} \text{ vp})\%$
Estimand 5.2	Ad26.COV2.S 2.5×10^{10} vp and Ad26.COV2.S 1×10^{10} vp	Relative VE = $100 \times (1 - \text{hazard ratio of incidence Ad26.COV2.S } 2.5 \times 10^{10} \text{ vp} / \text{Ad26.COV2.S } 1 \times 10^{10} \text{ vp})\%$
Between Cohorts:		
Estimand 5.3	Ad26.COV2.S 5×10^{10} vp (Cohort 1) and Ad26.COV2.S 5×10^{10} vp (Cohort 2)	Relative VE = $100 \times (1 - \text{hazard ratio of Cohort 1 Ad26.COV2.S } 5 \times 10^{10} \text{ vp} / \text{Cohort 2 Ad26.COV2.S } 5 \times 10^{10} \text{ vp})\%$

Estimand	Interventions	Summary Measures ¹
Estimand 5.4	Ad26.COV2.S 2.5×10^{10} vp (Cohort 1) and Ad26.COV2.S 2.5×10^{10} vp (Cohort 2)	Relative VE = $100 \times (1 - \text{hazard ratio of Cohort 1 Ad26.COV2.S } 2.5 \times 10^{10} \text{ vp} / \text{Cohort 2 Ad26.COV2.S } 2.5 \times 10^{10} \text{ vp})\%$
Estimand 5.5	Ad26.COV2.S 1×10^{10} vp (Cohort 1) and Ad26.COV2.S 1×10^{10} vp (Cohort 2)	Relative VE = $100 \times (1 - \text{hazard ratio of Cohort 1 Ad26.COV2.S } 1 \times 10^{10} \text{ vp} / \text{Cohort 2 Ad26.COV2.S } 1 \times 10^{10} \text{ vp})\%$

¹Relative VE and associated 95% CI will be calculated from Cox Proportional hazards model.

Analysis method will be repeated as explained in Section [5.3.2](#).

